7.6 Day 30 (\pm 14 days)

At Day 30 (\pm 14 days) the following study assessments should be performed:

- mRS (A telephone assessment may be conducted, but in-person is strongly encouraged)
- Device and/or Procedure Related AEs
- All SAEs
- All Deaths

Any death or device and/or procedure related AEs and all SAEs should be reported to Stryker Neurovascular within 24 hours of becoming aware. For all subjects who expire prior to the Day 30 assessment, available information regarding the primary cause of death and date/time of death will be recorded.

7.7 Day 90 (\pm 14 days)

At Day 90 (\pm 14 days) the following study assessments should be performed:

- mRS (A telephone assessment may be conducted, but in-person is strongly encouraged)
- EuroQol (EQ5D5L)
- Device and/or Procedure Related AEs
- All SAEs
- All Deaths

Any death or device and/or procedure related AEs and all SAEs should be reported to Stryker Neurovascular within 24 hours of becoming aware. For all subjects who expire prior to the Day 90 assessment, available information regarding the primary cause of death and date/time of death will be recorded.

Stryker Neurovascular

Document Title: ASSIST™ Registry Protocol

Document Number: CDM10001414

Rev: AB

Table 4. Time and Events Schedule

Time and Events Schedule						
Assessments:	Pre-procedure (Screening /Baseline)	Procedure	24 (-6/+24) hrs. post procedure	Discharge (or Day 5-7 whichever comes first)	Day 30 ±14 days	Day 90 ±14 days
Inclusion/Exclusion Criteria	✓					
Informed Consent*	✓					
Demographics & Medical History	✓					
Baseline Labs	✓					
mRS**	✓			✓	✓	✓
NIHSS Assessment	✓		✓	✓		
EuroQol (EQ5D5L)						✓
Stroke Onset	✓					
CT/MR ^Y	✓		✓			
Angiogram Procedure Information **** ^Y		✓				
Hospital Stay/Discharge Disposition****				✓		
Adverse Events [‡]		✓	✓	✓	✓	✓
Study Completion						✓

*Written Informed Consent must be obtained prior to subject enrollment and any data entry.

**Telephone mRS assessment is acceptable if subject is not able to return in person.

***See study binder for worksheets listing items to record during the procedure.

****Study Staff should review the study requirements with the subject and arrange all follow-up visits at discharge.

[‡] All AEs during procedure, only Device Related and/or Procedure Related AE & all SAE, death post procedure.

^Y CT/MR and Angiographic images will be de-identified with subject ID# if submitted to SNV or the core lab.

8 STATISTICAL METHODS

8.1 Sample Size Estimate and Justification

The sample size of ASSIST is based on the precision of the estimate of functional independence (90-day mRS 0-2) in a real-world setting. The TREVO Registry had an observed rate of 55.3% with a 95% CI of [53.1, 57.4] for functional independence and the rate is similar to that reported in a pooled analysis of 5 RCT thrombectomy trials (46.0%)⁷. Given the uncertainty of outcomes of some of the procedural techniques a rate of 50% functional independence was assumed for this study with a precision of 6%. With a 95% Wald

STRYKER CONFIDENTIAL - THIS DOCUMENT CONTAINS CONFIDENTIAL AND PROPRIETARY INFORMATION THAT IS THE PROPERTY OF STRYKER CORPORATION. NEITHER THIS DOCUMENT NOR THE INFORMATION HEREIN MAY BE REPRODUCED, USED, OR DISCLOSED TO ANY THIRD PARTY WITHOUT THE PRIOR WRITTEN CONSENT OF STRYKER CORPORATION.

Document Title: ASSIST™ Registry Protocol

Document Number: CDM10001414

Rev: AB

confidence interval of [47%, 53%], a sample size of 1200 observes such precision inference with a probability > 0.9 . A 20% loss to follow-up increases the total sample size to $1200/0.8 = 1500$.

There may not be uniform recruitment of patients to each technique group. Thus, a maximum of 5 groups was used to calculate the minimum and maximum sample size per group, given that additional techniques and commercialized devices may be added during the conduct of the study. Assuming a minimum group size of 72 and a total enrollment of 1500, the maximum enrollment in any technique group is $(1500 - 72) / 4 = 357$.

The overall sample size as well as minimum and maximum enrollment per technique provides sufficient sample size to provide precise estimates of the study endpoints in each of the procedural techniques.

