Inclusion Criteria	
1. Subjects who experienced acute ischemic stroke (AIS), eligible for restoration of blood flow using Stryker Neurovascular market-released products in the neurovasculature to remove thrombus2. Occlusion of intracranial anterior circulation vessel3. Subject or subject's legally authorized representative (LAR) has signed the informed consent form prior to or within 48 hours post-procedure4. Subject is willing to comply with the protocol follow-up requirements5. The intended technique and treated technique must be one of the following techniques for the first thrombectomy pass in the neurovasculature per Instructions For Use (IFU¹): 

Technique Category	Devices*	

SR Classic	SR + BGC	

SR Combination	SR + Asp Cath \pm Pump + BGC or LS	

Direct Aspiration	Asp Cath \pm Pump + BGC or LS	

 
*Defined devices must be SNV market-released products.
	Technique Category	Devices*	SR Classic	SR + BGC	SR Combination	SR + Asp Cath \pm Pump + BGC or LS	Direct Aspiration	Asp Cath \pm Pump + BGC or LS
Technique Category	Devices*								
SR Classic	SR + BGC								
SR Combination	SR + Asp Cath \pm Pump + BGC or LS								
Direct Aspiration	Asp Cath \pm Pump + BGC or LS								
Exclusion Criteria	The subject is participating in another device trial or any other clinical trial where the study procedure or treatment might confound this study's endpoint.								
Statistical Methods									
Statistical Test Method	Sample size is estimated based on the desired measurement precision of primary clinical and procedural outcomes. General summary and descriptive statistics will be used to analyze the study data. Logistic regression will be used to evaluate predictors of good outcomes in each of the techniques. Further details are provided in the Statistical Analysis Plan (SAP).								

STRYKER CONFIDENTIAL - THIS DOCUMENT CONTAINS CONFIDENTIAL AND PROPRIETARY INFORMATION THAT IS THE PROPERTY OF STRYKER CORPORATION. NEITHER THIS DOCUMENT NOR THE INFORMATION HEREIN MAY BE REPRODUCED, USED, OR DISCLOSED TO ANY THIRD PARTY WITHOUT THE PRIOR WRITTEN CONSENT OF STRYKER CORPORATION.

Stryker Neurovascular

Document Title: ASSIST™ Registry Protocol

Document Number: CDM10001414

Rev: AB

TABLE OF CONTENTS

1	Introduction and Rationale	9
1.1	Mechanical Thrombectomy Techniques	9

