7.5.1 Post Discharge Follow Up

The designated staff at the clinical site will review the follow-up schedule with the subject to maximize compliance. The staff will instruct subjects to return for follow-up assessments according to the study Time

STRYKER CONFIDENTIAL - THIS DOCUMENT CONTAINS CONFIDENTIAL AND PROPRIETARY INFORMATION THAT IS THE PROPERTY OF STRYKER CORPORATION. NEITHER THIS DOCUMENT NOR THE INFORMATION HEREIN MAY BE REPRODUCED, USED, OR DISCLOSED TO ANY THIRD PARTY WITHOUT THE PRIOR WRITTEN CONSENT OF STRYKER CORPORATION.

Document Title: ASSIST™ Registry Protocol

Document Number: CDM10001414

Rev: AB

and Events Schedule in Table 4. Study staff should establish a date for the follow-up visits with the subject and if possible, schedule the visits at the time of hospital discharge.

The study will be considered complete after all subjects have completed the Day 90 (\pm 14) follow-up assessments or have discontinued the study early. Requirements of each follow-up evaluation are detailed below.

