8.2 Statistical Analysis

Day 90 outcomes will be compared to pre-stroke mRS status, baseline imaging and time of symptom onset to treatment. Interim analysis will be performed periodically, and the results will be reported. Additional interim analyses and data reporting will occur throughout the study enrollment period.

Sub-group analyses for the Registry will be performed under guidance from the Study PIs, Steering Committee, and Sponsor.

General summary and descriptive statistics will be used to analyze the data. For each binary and categorical variable, procedural success, the point estimate, percentage, and its exact 95% confidence interval will be provided. For continuous variables, total sample size, mean, standard deviation, median, minimum, and maximum will be provided.

Logistic regression will be used to evaluate predictors of good outcomes in each of the techniques.

Further details will be provided in the SAP.

All statistical analyses will be performed using SAS version 9.4 or above. (Copyright © 2002-2008 by SAS Institute Inc., Cary, North Carolina, USA, all rights reserved)

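### Does raising enrolment from 1200 to 1500 leave the Day-90 mRS 0-2 rate exposed to bias from 20% loss to follow-up?

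*Combined protocol and SAP*

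**What the plan says.** Section 8.1 assumes a 50% rate of mRS 0-2 at Day 90 with a 95% Wald interval of 47% to 53%, and gives 1200 as the number needed. It continues: "A 20% loss to follow-up increases the total sample size to" 1500. Section 8.2 plans descriptive statistics. For binary variables, "the point estimate, percentage, and its exact 95% confidence interval will be provided". It adds: "Further details will be provided in the SAP". The synopsis makes the same deferral. Section 4.1 defines the primary clinical outcome separately for each technique.

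Several provisions limit loss. Under Section 7.5.1 site staff "will review the follow-up schedule with the subject to maximize compliance" and, if possible, "schedule the visits at the time of hospital discharge". A footnote to Table 4 says: "Telephone mRS assessment is acceptable if subject is not able to return in person". Deaths are collected at each follow-up contact. Section 7.7 provides that "For all subjects who expire prior to the Day 90 assessment, available information regarding the primary cause of death" is recorded, with the date and time. Section 6.2 records the reason for withdrawal but ends follow-up at that point, without replacement. Table 4 also schedules mRS at discharge and Day 30, and NIHSS at 24 hours and discharge.

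**The concern.** Allowing for 20% loss by dividing by 0.8 treats the loss as a matter of numbers only. If subjects without a Day-90 score have a different rate of good outcome from those with one, a percentage over followed subjects is biased by an amount that does not depend on N, and the exact interval will not show it.

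The design suggests one way this could happen. Deaths are actively sought, so they stay in the data as poor outcomes, while survivors can go missing. The followed group would then contain too many deaths and the rate would come out low. Loss concentrated among disabled survivors would push it the other way. Sections 8.1 and 8.2 do not say whether the denominator is all enrolled or all followed, what happens to a missing score, or that a death before Day 90 counts as not mRS 0-2. At stake is whether the pooled rate could be wrong by as much as the 3 points it was sized to resolve.

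**Working it through.** **Inputs.** From Section 8.1: rate 50%, 1200 followed, 20% loss, 1500 enrolled, technique groups of 72 to 357. From Section 2.1 (TREVO study): 90-day mortality 20%. From Section 2.5 (DAWN treatment arm): stroke-related mortality 17/107, about 16%. The outcome rate among lost subjects is not in the documents, so it is varied.

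**The plan's figure.** 1200/0.8 = 1500, as stated. The Wald half-width at 1200 is 1.96 × √(0.25/1200) = 2.83 points, inside the 3-point target. Without inflation, 0.8 × 1200 = 960 would be followed, with half-width 3.16 points. The inflation does its job.

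**Bias of a followed-only rate.** Bias = L × (followed rate − lost rate), where L is the fraction lost. N does not appear. At L = 0.20 a 3-point bias needs a gap of 3/0.20 = 15 points between followed and lost. At L = 0.10 it needs 30 points.

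**Deaths all known, survivors lost at random.** With true rate p and mortality m, bias = −p·m·L/[(1−m)(1−L)]. For p = 0.50:

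| Mortality | Loss | Bias (points) |
|---|---|---|
| 16% | 20% | −2.4 |
| 20% | 20% | −3.1 |
| 20% | 10% | −1.4 |
| 20% | 2% | −0.3 |

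In the two 20%-loss rows, the exact 95% interval on 1200 covers the true 50% about 63% and 43% of the time.

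**Other loss patterns.** Keep 20% mortality and 20% loss. Of 1500 enrolled, 750 have a good outcome and 300 survivors are lost. If the lost survivors have good-outcome rate q, the followed rate is (750 − 300q)/1200:
- q = 62.5% (lost at random): 46.9%, bias −3.1
- q = 50%: 50.0%, bias zero
- q = 40%: 52.5%, bias +2.5

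**Loss too small to matter.** With a true rate of 50%, the extreme case has every lost subject failing, so the followed rate is 0.50/(1 − L). This reaches 53% at L = 1 − 0.50/0.53 = 5.7%. If every lost subject succeeds, 47% is reached at the same L. Below about 5.7% loss a shift above 3 points cannot occur.

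**How much loss to expect.** Section 8.1 gives the TREVO Registry rate as 55.3% with interval 53.1 to 57.4, a half-width of 2.15 points. The Wald denominator is 1.96² × 0.553 × 0.447/0.0215² ≈ 2054, or 1971 to 2141 allowing for rounding. Section 2.4 gives 2008 treated. This suggests little loss there, though it is an inference from rounded figures.

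**Per technique.** A group of 357 leaves 0.8 × 357 ≈ 286 followed, half-width 5.8 points. A group of 72 leaves about 58, half-width 12.9 points. At a bias of −3.1 points, exact coverage is about 84% and 93%.

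**Would imputation settle it?** Take q = 40% and suppose no recorded variable predicts who is lost. Followed subjects have 750 − 120 = 630 good outcomes among 900 survivors, or 70%. Imputing 70% to the 300 lost gives (630 + 210)/1500 = 56.0%, against 52.5% from followed subjects alone and a true 50%. With survivors lost at random it returns (562.5 + 187.5)/1500 = 50.0%. Which estimate is better depends on a mechanism nobody knows in advance.

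**The case for a change.** The strongest case for a change is that the sponsor, with telephone assessment and visit scheduling in place, still allowed for 20% loss, and that at this figure even random loss among survivors gives a bias of about the planned half-width. The data for an imputation are already scheduled, so a rule would cost only wording and programming. Section 8.2 also promises interim results during enrolment, so the rule should be settled before results are seen. And Section 5.3 says the registry is meant to help compare techniques, so loss that differs by technique could distort the comparison.

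The principle stands: inflation does not address bias, and the reviewed text does not write down the denominator or the rule for deaths. It also stands that these should be settled before the first report. What does not follow is that the plan is wrong. Section 8.1 makes no claim about bias, no stated rule is shown to give a wrong answer, and denominators and missing-data rules are normal SAP content. The 20% is a planning allowance, and the closest precedent in the document points lower. The text offers no evidence that loss will differ by technique.

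**Conclusion.** No change to the plan follows. This is detail not written in the protocol and deferred to the SAP. The sample size calculation is correct for its purpose. The possible bias has unknown sign. It comes near 3 points for the pooled rate only with loss close to 20%, a followed-only denominator that the plan does not state, and an assumed pattern of loss. It is about -0.3 points at 2% loss with 20% mortality, and cannot exceed 3 points below about 5.7% loss when the true rate is 50%. For the primary outcome by technique it is smaller than the random error in every group size considered. The registry is descriptive, with no hypothesis test or decision threshold attached to this rate.

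Counting a known death as not mRS 0-2 is what an analyst would do in any case; the document's own accounts of MR CLEAN and DAWN (Sections 2.3 and 2.5) already place death on the mRS scale. Stating the denominator, tabulating missing scores by technique and showing bounds for the lost group are things competent analysts can be expected to supply. Making imputation the main estimate would be a trade-off with no assured gain, since it can land further from the truth than the simple rate. Because the SAP text was not available, this conclusion does not say what the SAP contains; a reader who holds it can check that the denominator and the death rule are stated there.

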8.2 Statistical Analysis

Day 90 outcomes will be compared to pre-stroke mRS status, baseline imaging and time of symptom onset to treatment. Interim analysis will be performed periodically, and the results will be reported. Additional interim analyses and data reporting will occur throughout the study enrollment period.

Sub-group analyses for the Registry will be performed under guidance from the Study PIs, Steering Committee, and Sponsor.

General summary and descriptive statistics will be used to analyze the data. For each binary and categorical variable, procedural success, the point estimate, percentage, and its exact 95% confidence interval will be provided. For continuous variables, total sample size, mean, standard deviation, median, minimum, and maximum will be provided.

Logistic regression will be used to evaluate predictors of good outcomes in each of the techniques.

Further details will be provided in the SAP.

All statistical analyses will be performed using SAS version 9.4 or above. (Copyright © 2002-2008 by SAS Institute Inc., Cary, North Carolina, USA, all rights reserved)

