4.5 Safety Outcomes

1. All-cause mortality and stroke-related mortality up to Day 90 (± 14)
2. Device and/or procedure related SAEs up to Day 90 (± 14)
3. Neurological deterioration at 24 (-6/+24) hours post procedure defined as a four or more point increase in NIHSS from baseline
4. Symptomatic intracranial hemorrhage (SICH) adapted from European Cooperative Acute Stroke Study (ECASSIII) as any apparent extravascular blood in the brain or within the cranium that is associated with clinical deterioration defined by a NIHSS increase of four points or more from baseline up to 24 (-6/+24) hours
5. Embolization to New Territory adjudicated by core lab

Document Title: ASSIST™ Registry Protocol

Document Number: CDM10001414

Rev: AB

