6.2 Withdrawal and Replacement of Subjects

While study withdrawal is discouraged, subjects may withdraw from the study at any time, with or without reason and without prejudice to further treatment. Withdrawn subjects will not undergo any additional follow-up, nor will they be replaced. If a subject chooses to withdraw from the Registry, the reason(s) for withdrawal will be recorded on the appropriate electronic Case Report Form (eCRF) and in the medical record.

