12 ADVERSE EVENTS

An Adverse Event (AE) is any untoward medical occurrence, unintended disease or injury, or untoward clinical sign (including abnormal laboratory findings) in subjects, users or persons, whether or not related to the medical device(s). All subjects will be assessed for complications or adverse events during the procedure and at all follow-up visits per section 7.4-7.7, and recorded on the AE case report form. Data to be collected will include the AE event term, onset and resolution dates (or whether the AE is ongoing), seriousness, management/treatment, outcome, and determination of the relationship to the devices and the index procedure. All AEs will be followed until resolution or an appropriate endpoint is reached, or until the subject has completed or discontinued the registry.

More specifically, the following adverse events are to be reported on the Adverse Event case report form:

- All AEs and serious adverse events (SAE) that occur during the procedure
- Only device and/or procedure related AEs post procedure through Day 90
- All SAEs post procedure through Day 90

STRYKER CONFIDENTIAL - THIS DOCUMENT CONTAINS CONFIDENTIAL AND PROPRIETARY INFORMATION THAT IS THE PROPERTY OF STRYKER CORPORATION. NEITHER THIS DOCUMENT NOR THE INFORMATION HEREIN MAY BE REPRODUCED, USED, OR DISCLOSED TO ANY THIRD PARTY WITHOUT THE PRIOR WRITTEN CONSENT OF STRYKER CORPORATION.

Stryker Neurovascular

Document Title: ASSIST™ Registry Protocol

Document Number: CDM10001414

Rev: AB

NOTE: Any “prolonged” hospitalization(s) related to the study procedure which is considered standard of care due to subject age, co-morbidities or neurological status at presentation will not be considered SAEs

- Any event causing neurological deterioration defined as a ≥ 4 point increase on the NIHSS from baseline (e.g. cerebral edema, brain herniation, stroke progression) which is related to the index stroke
- Any event causing symptomatic intracranial hemorrhage (SICH) defined as a ≥ 4 point increase in NIHSS from baseline for which the hemorrhage is determined to be the cause
- All device-related adverse events (also known as “adverse device effects” [ADEs])
- All serious adverse device effects (SADEs)
- All unanticipated serious adverse device effects (USADEs)
- All adverse events that result in death through Day 90

NOTE: Death should not be recorded as the AE term but should be reflected as an outcome to a specific AE

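### The only stated rule that reaches 90-day mortality, a percentage with an exact interval, takes no account of incomplete follow-up.

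*Combined protocol and SAP*

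**What the plan says.** Section 4.5 of the protocol lists "All-cause mortality and stroke-related mortality up to Day 90" as safety outcome 1, with a window of 14 days either side. Section 8.2 does not name mortality. Its general rule is: "For each binary and categorical variable, procedural success, the point estimate, percentage, and its exact 95% confidence interval will be provided". The section then adds: "Further details will be provided in the SAP". No SAP text is part of the document reviewed. The pages supplied contain no survival method, censoring rule, mortality denominator or rule for unknown vital status.

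Four provisions make follow-up unequal:

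- Section 8.1 inflates the sample size for incomplete follow-up: "A 20% loss to follow-up increases the total sample size to" 1500.
- Section 6.2: "Withdrawn subjects will not undergo any additional follow-up, nor will they be replaced".
- Section 7.5.1 counts the study as complete once every subject has had the Day 90 assessment "or have discontinued the study early".
- Section 7.7 places the last visit between Day 76 and Day 104.

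On data, section 12 asks sites to report "All adverse events that result in death through Day 90". Sections 7.4 to 7.7 collect deaths at each follow-up contact, with available information on primary cause and on date and time.

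**The concern.** A death before loss is seen and counted. Every subject who is lost was alive when last seen. A denominator of known-status subjects therefore removes only people who were alive at last contact, and the rate tends to be too high. A denominator of all enrolled treats every lost subject as a survivor, and the rate tends to be too low. The exact interval covers binomial sampling error only, so it does not show this error.

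The final-visit window adds a second problem, because status at the last visit refers to a different day for different subjects. For stroke-related death, deaths from other causes are a competing event.

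Mortality will be read beside the earlier studies in section 2. Section 8.2 also promises periodic interim reports during enrollment. If those include subjects who have not yet reached Day 90, follow-up is incomplete even with no loss at all.

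**Working it through.** **Inputs from the protocol.** Evaluable sample 1200 and loss 20% (section 8.1); final visit Day 76 to 104 (section 7.7); group sizes 72 and 357 (section 8.1). For the level of mortality, 20.0% at 90 days in the earlier single-arm study (section 2.1).

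**Assumptions, not in the protocol.** 70% of 90-day deaths fall evenly over Days 0 to 14 and the rest evenly over Days 14 to 90. Loss times are even over Days 7 to 60 and independent of death.

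**Plan's own figure.** 1200/(1 − 0.20) = 1500, as stated. No precision is stated for mortality.

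**Step 1. Share of deaths seen before loss.** Let F(t) be the share of 90-day deaths by day t: F(t) = 0.05t up to Day 14, then 0.7 + 0.3(t − 14)/76. Averaged over loss times:

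E[F] = [0.025(14² − 7²) + 0.7 × 46 + (0.3/76)(46²/2)]/53 = (3.675 + 32.2 + 4.176)/53 = 0.756.

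**Step 2. The two crude rates.** Let M be true mortality and q the share assigned a loss time.

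- All enrolled: A = M[1 − q(1 − E[F])].
- Known status: K = A/[A + (1 − M)(1 − q)].
- Share actually lost: q(1 − M·E[F]), smaller than q because some die first.

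For 20% actually lost at M = 0.20, q = 0.20/(1 − 0.20 × 0.756) = 0.2356.

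| Share assigned loss | Actually lost | Known status | All enrolled |
|---|---|---|---|
| 5% | 4.2% | 20.6% | 19.8% |
| 10% | 8.5% | 21.3% | 19.5% |
| 20% | 17.0% | 22.9% | 19.0% |
| 23.6% | 20.0% | 23.6% | 18.8% |

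Example, last row: A = 0.20(1 − 0.2356 × 0.2443) = 0.1885, and K = 0.1885/0.80 = 0.2356. Simulation of this row gives 23.6% to 23.7% and 18.9%. Kaplan-Meier at Day 90 averages 20.0% to 20.1%, as it must when loss is independent of death.

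**Step 3. Other timings.** With q = 20% and loss spread over Days 6 to 90, known-status runs from 22.1% to 23.2% and all-enrolled from 18.1% to 19.3%, depending on how early deaths occur. At the extremes:

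- Loss right after the procedure: known-status 20.0% (unbiased), all-enrolled 0.20 × 0.80 = 16.0%.
- Loss just before Day 90: all-enrolled 20.0% (unbiased), known-status 0.20/(0.20 + 0.80 × 0.80) = 23.8%.

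**Step 4. Against the reported uncertainty.** Exact 95% half-widths at about 20% are ±2.1 points (n = 1500), ±2.3 (n = 1200), ±4.3 (n = 357) and ±9.7 (n = 72). With 20% actually lost, the known-status error is 23.6 − 20.0 = 3.6 points and exceeds the pooled half-width. The all-enrolled error is 20.0 − 18.8 = 1.2 points and does not. With q = 20%, simulated coverage of the nominal 95% interval is 29% (known status) and 84% (all enrolled).

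**Step 5. Visit window.** If status is read at the visit rather than at Day 90, and the late death rate carries on past Day 90, a true 20% becomes 0.20 × (0.7 + 0.3 × 62/76) = 18.9% at Day 76 and 0.20 × (0.7 + 0.3 × 90/76) = 21.1% at Day 104. With deaths spread evenly it becomes 0.20 × 76/90 = 16.9% and 0.20 × 104/90 = 23.1%.

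**Step 6. Bounds without assumptions on loss.** With 240 deaths among 1200 known and 300 unknown, mortality lies between 240/1500 = 16.0% and 540/1500 = 36.0%.

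**The case against.** A reader might infer several stronger claims that the protocol does not support.

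- *That the plan prescribes crude mortality.* Section 8.2 states a general rule, does not name mortality and leaves detail to the SAP. A SAP could name a survival method. This stands: the point concerns the only rule in the text supplied.
- *That the rate is biased whichever denominator is used.* Not without conditions. One denominator becomes nearly unbiased when loss is immediate, the other when it is very late.
- *That 20% will have unknown vital status.* The figure is a planning allowance for the 90-day mRS. The mRS may be taken by telephone at Days 30 and 90, and deaths are to be reported within 24 hours of awareness. Loss for vital status may be smaller, and the error shrinks with it.
- *That section 12 stops collecting deaths at Day 90, so horizons cannot be aligned.* Its item on fatal events does not say that only those are collected, and section 7.7 records date and time for deaths before the Day 90 assessment, even one held late. Later deaths can be cut at Day 90. Survivors last seen on Days 76 to 89 remain uncertain.
- *That comparisons between techniques are seriously distorted.* In groups of 72 to 357 the error is smaller than the half-width, and similar loss across techniques would largely cancel.
- *That Kaplan-Meier is simply correct.* It assumes loss unrelated to risk of death, and the simulation builds this in.

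It is also fair that the late-window trial in section 2.5 gives stroke-related mortality as crude proportions, so a crude rate is the like-for-like figure there. That supports showing both.

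**Conclusion.** The concern holds in limited form. The one stated rule that reaches 90-day mortality ignores incomplete follow-up, which the plan itself expects. Under independent loss, the known-status rate generally errs upward and the all-enrolled rate downward. At a true 20%, the gap between them is about 5 points if 20% are actually lost (23.6% against 18.8%) and about 1 to 2 points if 5% to 10% are assigned a loss time. These sizes rest on assumed death and loss timing. The consequence is mainly for the pooled rate, where the known-status error can exceed the reported interval. This is more than missing detail: a better estimator is available from death dates that the registry already plans to record. The change should be made, but it does not undermine the design.

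**What to change.** State in section 8.2 or the SAP:

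1. All-cause mortality is the Kaplan-Meier estimate at a fixed Day 90 with a log-log 95% interval, censoring at last contact known alive.
2. Stroke-related mortality is the Aalen-Johansen cumulative incidence at Day 90, with other death as the competing event.
3. The same Day 90 cut applies to every subject, using recorded death dates and not the visit date.
4. The crude proportion is shown alongside, with its denominator and the number of unknown vital status, for comparison with earlier studies.
5. The assumption that loss is unrelated to risk of death is stated, with a best/worst-case analysis in which all subjects of unknown status are counted first as alive and then as dead.

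The cost is slightly more analysis work with standard SAS procedures. The only added data item is the date of last contact known alive, if the eCRF does not already hold it.

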5.1 Sites

The Registry will enroll up to 1500 subjects and will be conducted at up to 100 sites worldwide. The Registry devices will have regulatory authorization to be on the market in the geographic location of all sites.

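### The planned exact 95% intervals and the 47-53% precision ignore site: if outcomes correlate positively within site, they under-cover as inference beyond the participating sites

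*Combined protocol and SAP*

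**What the plan says.** Section 8.1 bases the sample size on precision alone: "a rate of 50% functional independence was assumed for this study with a precision of 6" (per cent). The interval that goes with this shows that the 6 points are the full width: "confidence interval of [47%, 53%], a sample size of 1200 observes such precision inference with a probability > 0.9". Loss to follow-up is then added: "A 20% loss to follow-up increases the total sample size to" 1500. The formula is a one-sample Wald interval with no design effect.

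Section 8.2 names the method for reporting: "For each binary and categorical variable, procedural success, the point estimate, percentage, and its exact 95% confidence interval will be provided". For modelling it says "Logistic regression will be used to evaluate predictors of good outcomes in each of the techniques", with no site term. Further detail is left to the SAP, but the text available contains no SAP provision on site.

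Section 5.1 gives the structure of the data: "The Registry will enroll up to 1500 subjects and will be conducted at up to 100 sites worldwide".

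**The concern.** An exact binomial interval has its nominal coverage when subjects are independent. Subjects treated at one hospital share operators, workflow and, for 90-day mRS, local raters, because no central mRS assessment is described. Core-lab reading of eTICI removes the rater effect but not the operator effect. Some positive within-site correlation is therefore plausible, although the documents do not quantify it.

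Precision is the only stated basis for the sample size, so the confidence interval is the registry's main inferential product. Section 5.3 gives comparison of techniques as an intent, and Section 4 foresees use of the data in regulatory and reimbursement files. An interval labelled 95% that covers less would make the estimates look firmer than they are. A site effect in the logistic regression would not repair this, because the descriptive intervals are computed separately.

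**Working it through.** **Inputs from the documents.** Rate 50%, target half-width 3 points, 1200 evaluable and 1500 enrolled (Section 8.1); at most 100 sites (Section 5.1). This gives 1500/100 = 15 enrolled and 1200/100 = 12 evaluable per site at the maximum number of sites.

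**Inputs assumed.** The ICC and the spread of site sizes. The documents give neither, so ranges are shown.

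**Step 1: the plan's own figure.** Wald half-width = 1.96 × √(0.25/1200) = 2.83 points, an interval of 47.2% to 52.8%, inside the target. The probability that the Wald width is at most 6 points at n = 1200 and a true rate of 50% is 1.00, so the stated probability above 0.9 is met. 1200/0.8 = 1500. The plan's figures reproduce under independence. The exact interval at 600/1200 is 47.1% to 52.9%, a half-width of 2.87.

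**Step 2: the slack.** Break-even design effect = (3/2.829)² = 1.125. With design effect = 1 + (m − 1) × ICC and m = 12, the break-even ICC is 0.1245/11 = 0.011. Starting from the exact interval's half-width, it is about 0.009.

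**Step 3: 90-day mRS 0-2, 100 equal sites of 12.** Half-width = 2.829 × √(design effect). Coverage of the unadjusted exact interval was simulated with a beta-binomial model (40,000 replicates).

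| Assumed ICC | Design effect | Half-width (points) | Simulated coverage |
|---|---|---|---|
| 0 | 1.00 | 2.83 | 95.4% |
| 0.01 | 1.11 | 2.98 | 93.9% |
| 0.02 | 1.22 | 3.12 | 92.9% |
| 0.05 | 1.55 | 3.52 | 88.9% |

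**Step 4: fewer or unequal sites.** The 100 sites are a ceiling. Break-even ICC = 0.1245/(m − 1):
- 75 sites (m = 16): 0.008
- 50 sites (m = 24): 0.005
- 30 sites (m = 40): 0.003
- 100 sites with a coefficient of variation of site size of 0.8: the design effect is 1 + ((1 + 0.64) × 12 − 1) × ICC, so the break-even is 0.1245/18.68 = 0.007

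**Step 5: first-pass eTICI 2c or better.** This is measured at the procedure, so the 20% loss need not apply. Section 8.1 gives no rate for it; 50% is assumed, which gives the widest interval. With all 1500 evaluable, half-width = 1.96 × √(0.25/1500) = 2.53 points, break-even design effect = (3/2.530)² = 1.406, and break-even ICC = 0.406/14 = 0.029.

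**Step 6: technique level, illustration only.** Take the 357 in Section 8.1 less 20%, about 286 evaluable, and suppose they come from 20 sites (m = 14.3). Under independence the half-width is 1.96 × √(0.25/286) = 5.8 points. At ICC 0.02 the design effect is 1.266 and the half-width 6.5. At ICC 0.05 they are 1.665 and 7.5. The 20 sites are an assumption.

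**The case against.** The strongest reply is that under-coverage needs two things the documents do not state: a positive ICC and a target wider than the participating sites. Section 8.2 calls the analysis descriptive. If the interval is meant to describe the sites that took part, a simulation with 100 sites of 12 gives coverage of the participating-site mean of about 95.6% at ICC 0.02 and 95.8% at 0.05, so nothing is lost. This stands as a condition on the point. It does not remove it, because Section 8.1 sets the precision for practice in the real world, which reaches beyond the enrolled sites.

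The effect is also modest in the favourable case. With 100 equal sites the target is still met at ICC 0.01 and missed by 0.12 points at 0.02. At technique level, a group of 72 already has a half-width of 11.5 points under independence, so site correlation is secondary there. Both points stand.

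The deferral to the SAP helps only in part. An adjusted interval could be added there, but Section 8.2 has already named the method.

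Three stronger readings are tempting and are not supported:
- A reader might infer that the intervals are too narrow and the 47-53% precision lost as a matter of fact. With no ICC given, this holds only under an assumption.
- A reader might infer that the problem must be worse by technique because techniques cluster in certain sites. Section 7.3.2 says that device approvals differ by region, which makes uneven use possible, but the documents do not describe how techniques are spread over sites.
- A reader might infer that every interval, including those for safety events, should be replaced. An intercept-only logistic GEE has no finite estimate when there are no events, and robust variance is unreliable with few sites.

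**Conclusion.** The point holds in conditional form. Sections 8.1 and 8.2 treat subjects as independent, and no text available adjusts for site. With positive within-site correlation, and with the intervals read as inference beyond the participating sites, nominal 95% intervals for 90-day mRS 0-2 would cover about 94% to 89% over ICC 0.01 to 0.05 at 100 equal sites. The 3-point margin has room for a design effect of only 1.125; fewer or unequal sites use it up at a smaller ICC. First-pass eTICI has more room if follow-up loss does not affect it. The size at technique level cannot be established from the documents. The 1200 and 1500 are not arithmetic errors; they are correct under independence. This is an inexpensive improvement to the analysis plan, not a flaw that undermines the design.

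**What to change.** In Section 8.2 or the SAP, for the two primary outcomes, overall and by technique, report a site-cluster-adjusted 95% interval next to the planned exact interval. One suitable form is the exact interval computed on the effective sample size, n divided by the estimated design effect, with site as the cluster. Keep the exact interval alone for rare safety events and for groups drawn from few sites, and say in advance how few is too few.

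In Section 8.1, state that the 47-53% precision assumes independent subjects, or give the half-width over a stated range of ICC, as in the table above.

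The cost is a few lines of analysis code, some wording and slightly wider reported intervals. No extra subjects or data are needed. If the ICC proves negligible, the two intervals will be close and little is lost.
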